### 6.6.2.2. Protocol Deviations

Protocol deviations will be compiled prior to database lock and will be summarized by category (n[%]) for the Safety Analysis Set. Categories will be assigned by the study Clinician.

In addition, protocol deviations related to COVID-19 may be presented in a separate listing if there is significant impact of COVID-19.

### 6.6.3. Study Intervention Exposure

Exposure will be summarized based on the Safety Analysis Set.

#### Exposure to PF-06863135

PF-06863135 is administered as a subcutaneous injection once every week on Days 1, 8, 15 and 21 of each 28-day cycle (a minimum of 6 days should be maintained between doses) except the first dose will be administered on Cycle 0 Day 1, which will serve as a priming dose. The dose interval will be changed from QW to Q2W in participants with a durable response (PR or better persisting for  $\geq 2$  months) who received at least 6 cycles of therapy. If the participant subsequently begins to have an increase of disease burden not yet qualifying as PD according to IMWG criteria, dose intervals should return to weekly dosing. If the dose interval is changed, cycles should remain the same length (ie, 4-week cycles).

The summary of treatment exposure to PF-06863135 will include the following information:

- Treatment duration (weeks) and planned treatment duration (weeks);
- Number of cycles started per participant (mean, median, min, max);
- Number and percent of participants starting a cycle (any cycle, cycle 0, 1, 2, 3, 4, 5, 6, 7, 8, 9, 10, 11,  $\geq 12$  cycles);
- Total number of doses received;
- Total cumulative dose (mg);
- Total planned cumulative dose (mg);
- Overall dose intensity (mg/week);
- Overall planned dose intensity (mg/week);
- Overall relative dose intensity (%);
- Number and percent of responding participants after 6 cycles who switched from QW to Q2W;

- The duration of PF-06863135 (in weeks) during the study for a participant is defined as:
  - Treatment duration (weeks) = (minimum of [last dose date + 7, death date] – first dose date)/7, if the last dose occurred in a cycle with QW dosing;
  - Treatment duration (weeks) = (minimum of [last dose date + 14, death date] – first dose date)/7, if the last dose occurred in a cycle with Q2W dosing.

The total cumulative dose (mg) of PF-06863135 is the sum of the actual doses that the participant received during the study; the cumulative dose (mg) of PF-06863135 per cycle is the sum of the actual doses that the participant received within that cycle (ie, total dose administered [mg]).

Planned treatment duration is needed to calculate dose intensity (DI) and relative dose intensity (RDI). It is defined as follows:

$$\text{Planned treatment duration (weeks)} = 1 \text{ (1 week for Cycle 0) + number of cycles started} \times 4.$$

The DI and the RDI will be calculated for each participant across all cycles and also for each individual cycle as follows:

Overall:

- Overall DI (mg/week) = Total cumulative dose (mg)/[treatment duration (in weeks)];
- Overall Planned DI (mg/week) = Total planned dose (mg)/(planned treatment duration in weeks);
- Overall RDI (%) = [Overall DI (mg/week) / Overall Planned DI (mg/week)] × 100.

By Cycle:

- Cycle DI (mg/week) = Cumulative dose for a given cycle (mg)/[actual cycle duration (in weeks)];
- Cycle Planned DI (mg/week) = Total planned dose for a given cycle (mg)/4 weeks;
- Cycle RDI (%) = [Cycle DI (mg/week) / Cycle Planned DI (mg/week)] × 100.

The planned dose by cycle is defined as

Cycle 0:

- Planned dose (mg/cycle) = Priming dose.

After Cycle 0:

- If the participant is on QW dosing schedule for the cycle:  
Planned dose (mg/cycle) = Full dose × 4.
- If the participant is on Q2W dosing schedule for the cycle:  
Planned dose (mg/cycle) = Full dose × 2.

Cycle DI and Cycle RDI will be summarized and plotted vs time (weeks).

**Exposure to Nirogacestat (Sub-study A)**

Nirogacestat is administered orally twice daily (BID) at 100 mg dose level in 28-day cycle.

The summary of treatment exposure to nirogacestat will include the following information:

- Treatment duration (weeks) and planned treatment duration (weeks);
- Total cumulative dose (mg);
- Total planned cumulative dose (mg);
- Overall dose intensity (mg/week);
- Overall relative dose intensity (%).

The duration of nirogacestat (in weeks) during the study for a participant is defined as:

$$\text{Treatment duration (weeks)} = (\text{last dose date of nirogacestat} - \text{first dose date of nirogacestat} + 1) / 7$$

The cumulative dose (mg) of nirogacestat is the sum of the actual dose levels that the participant received during the study (ie, total dose administered [mg]).

The DI and RDI of nirogacestat will be calculated for each participant during the study. The DI (mg/week) of nirogacestat is defined as

$$\text{DI (mg/week)} = [\text{cumulative dose (mg)}] / [\text{treatment duration (weeks)}]$$

The RDI of nirogacestat is defined as the ratio of the DI and planned dose intensity and expressed in %

$$\text{RDI (\%)} = 100 \times [\text{DI (mg/week)}] / [7 \times 2 \times 100 \text{ (mg/week)}].$$

### 6.6.3.1. Dose Reductions, Interruptions, and Delays

#### **Dose Reduction**

For PF-06863135 and nirogacestat, a dose reduction is defined as a non-zero dose that is less than the prior dose and less than the planned dose in the protocol.

The number and percentage of participants with at least 1 dose reduction as well as a breakdown of dose reductions (1/2/3/ $\geq$ 4) will be summarized.

#### **Dose Interruption**

For PF-06863135, an interruption is defined as missing a scheduled dose based on the planned dosing frequency (QW or Q2W).

For nirogacestat, an interruption is defined as a 0 mg dose administered on 1 or more days. (Note: A dose interruption is not considered a dose reduction).

What follows defines how dose interruptions of nirogacestat will be counted in the case of multiple dose interruptions:

- If an interruption occurs consecutively for at least 2 days due to the same reason, then it will be counted only once (example: If the actual dose on Days 1-3 is 100 mg BID and actual dose on Days 4-5 is 0 mg and dose interruption on Days 4-5 is due to AE, then the total number of dose interruptions is 1).
- If an interruption occurs consecutively for at least 2 days due to different reasons, then it will be counted for each reason (example: If the actual dose on Days 1-3 is 100 mg and actual dose on Days 4-5 is 0 mg and dose interruption on Day 4 is due to AE and dose interruption on Day 5 is due to dosing error, then the total number of dose interruptions is 2).
- If an interruption occurs for more than 1 day due to the same reason, but the days are not consecutive, ie, there is at least 1 dosing day in between, then each dose interruption will be counted as a different occurrence (example: if the actual dose on Days 1, 3, and 5 is 100 mg BID and actual dose on Days 2 and 4 is 0 mg, and dose interruptions on Day 2 and 4 are both due to dosing error, the total number of dose interruptions is 2).

The number and percentage of participants with dose interruptions as well as a breakdown of dose interruptions (1/2/3/ $\geq$ 4) will be summarized. Percentages will be calculated based on the total number of participants in the Safety Analysis Set.

### **Dose Delay**

Section 12.10.2 in the protocol specifies that if PF-06863135 cannot be administered on the planned day, it should be skipped until the next planned dose (ie, if Day 15 dose cannot be administered, the dose should be skipped until Day 22). Therefore, dose delay is not applicable to PF-06863135 per protocol.

Dose delay is not applicable to nirogacestat (sub-study A).

### **6.6.4. Concomitant Medications and Nondrug Treatments**

The following analyses will be based on the Safety Analysis Set.

**Concomitant medications** are medications, other than study medications, which started prior to first dose date of study intervention and continued on during the on-treatment period as well as those started during the on-treatment period. **Prior medications** are medications, other than study medications, which are started before the first dose of study intervention.

Prior and concomitant medications will be summarized from the ‘Prior and Concomitant Medications’ eCRF page. **Pre-medications** required for CRS will also be summarized separately from the ‘Pre-Medication Treatment’ eCRF page.

Summary of prior medications, concomitant medications and summary of pre-medications will include the number and percentage of participants by Anatomical Therapeutic Chemical (ATC) Classification Level 2 and preferred term. A participant will be counted only once within a given drug class and within a given drug name, even if he or she received the same medication at different times. If any prior or concomitant medication is classified into multiple ATC classes, the medication will be summarized separately under each of these ATC classes. The summary tables will be sorted in descending frequency of ATC class and descending frequency of drug name in a given ATC class in Phase 2. In case of equal frequency regarding ATC class (respectively drug name), alphabetical order will be used. Medications without an ATC classification Level 2 coded term will be summarized under the ‘Unavailable ATC classification’ category.

### **6.6.5. Subsequent Anticancer Therapies**

The following analyses will be based on the Safety Analysis Set.

Subsequent anticancer drug treatment will be provided in a data listing with data retrieved from ‘Follow-up Cancer Therapy’ eCRF page.

Number and percentage of participants with any anticancer therapy after discontinuation of study intervention will be tabulated overall and by type of therapy based on the data collected from the ‘Response to Regimen – Follow-up Cancer Therapy’, ‘Non-drug Treatments – Follow-up Radiation’, ‘Follow-up Cancer Surgery’ eCRF pages.

### **6.7. Safety Summaries and Analyses**

The Safety Analysis Set will be the primary population for safety evaluations. Summaries of AEs and other safety parameters will be based on the Safety Analysis Set.

090177e196913362\Approved\Approved On: 19-Mar-2021 12:41 (GMT)

### 6.7.1. Adverse Events

All analyses will be based on treatment emergent adverse events (TEAE) unless otherwise specified. Treatment emergent is defined in [Section 3.5](#). AEs not considered treatment emergent will be flagged in data listings. Summaries of TEAEs due to COVID-19 may be produced if appropriate.

A high-level summary of adverse events (all causality and treatment-related, separately) will include the number and percent of participants with:

- Any TEAE;
- Serious TEAE;
- TEAE with CTCAE Grade 3-4;
- Grade 5 TEAE;
- TEAEs leading to dose interruptions of PF-06863135;
- TEAEs leading to dose interruptions of the combination partner agent (presenting the study drug name in the summary table);
- TEAEs leading to dose reductions of PF-06863135;
- TEAEs leading to dose reductions of the combination partner agent;
- TEAEs leading to withdrawal of PF-06863135;
- TEAEs leading to withdrawal of the combination partner agent;
- TEAEs leading to withdrawal of all study drugs;
- CRS;
- ICANS.

Related TEAEs will be summarized by each individual study drug as follows:

- Related to any study drug;
- Related to PF-06863135;
- Related to the combination partner agent (presenting the study drug name in the summary table).

Seriousness, toxicity grade, action taken (interruption, reduction, and withdraw) are as reported by the investigator on the adverse event CRF.

Summaries by SOC and PT in descending order of the frequency in Phase 2 will be provided for:

- TEAEs (all causality);
- TEAEs by maximum toxicity grade (all causality);
- TEAEs (treatment-related);
- TEAEs by maximum toxicity grade (treatment-related);
- TEAEs leading to death (all causality);
- TEAEs leading to death (treatment-related);
- TEAEs leading to dose interruption of PF-06863135 (all causality);
- TEAEs leading to dose interruption of PF-06863135 (treatment-related);
- TEAEs leading to dose interruption of the combination partner agent (all causality);
- TEAEs leading to dose interruption of the combination partner agent (treatment-related);
- TEAEs leading to dose reduction of PF-06863135 (all causality);
- TEAEs leading to dose reduction of PF-06863135 (treatment-related);
- TEAEs leading to dose reduction of the combination partner agent (all causality);
- TEAEs leading to dose reduction of the combination partner agent (treatment-related);
- TEAEs leading to withdrawal of PF-06863135 (all causality);
- TEAEs leading to withdrawal of PF-06863135 (treatment-related);
- TEAEs leading to withdrawal of the combination partner agent (all causality);
- TEAEs leading to withdrawal of the combination partner agent (treatment-related);
- Serious TEAEs (all causality);
- Serious TEAEs (treatment related).

An event will be considered treatment related if the investigator considered the event related to one or both of study drugs given in combination, or if relationship is missing. Each participant will be counted only once within each SOC and PT.

The following summaries will be provided by PT only (ie, summaries will not include SOC) in descending order of the frequency in Phase 2 for:

- Most common TEAEs by PT and maximum severity grade (All grades, Grade 3-4 and Grade 5) (all causality);
- Most common TEAEs by PT and maximum severity grade (All grades, Grade 3-4 and Grade 5) (treatment-related);
- TEAEs (all causality);
- TEAEs (treatment-related);
- Serious TEAEs (all causality);
- Serious TEAEs (treatment-related).

Each participant will be counted only once within each PT.

In case a participant has events with missing and non-missing toxicity grades, the maximum of the non-missing grade will be displayed. Missing grade will only be displayed in the event that only 1 event has been reported for a participant and the grade is missing.

#### **6.7.1.1. Adverse Events of Special Interest**

For all sub-studies, CRS and ICANS are adverse event of special interest (AESI) and will be assessed (including severity assessment) according to ASTCT criteria. Both CRS and ICANS will be collected on the AE CRF page and coded using the most current version of MedDRA. CRS will have the PT coded as “cytokine release syndrome”, and ICANS will have the PT coded as “immune effector cell-associated neurotoxicity syndrome”.

A high-level summary of each AESI (CRS and ICANS) will include the number and percent of participants with:

- Any AESIs;
- Serious AESIs;
- AESIs with CTCAE Grade 3-4;
- Grade 5 AESIs;
- AESIs leading to dose interruption of PF-06863135 and the combination partner agent;
- AESIs leading to dose reduction of PF-06863135 and the combination partner agent;

- AESIs leading to permanent withdrawal of PF-06863135 and the combination partner agent.

In addition, time to onset of the AESI, and time to resolution of the AESI (in days) will be summarized with descriptive statistics (mean, median, standard deviation, minimum, and maximum).

A summary of AESI symptoms as collected from ‘CRS AE’, ‘ICANS’ and ‘ICE’ CRFs will be provided. Time to onset of the AESI symptoms, and time to resolution of the AESI symptoms (in hours and/or in days as appropriate) will be summarized.

A listing of AESI with supportive information will also be provided.

### **6.7.2. Deaths**

The frequency (number and percentage) of participants in the Safety Analysis Set who died at any time and who died within 28 days after last dose of study intervention as well as the primary and secondary reason for death, will be tabulated based on information from the ‘Death Details’ and ‘Survival Follow-Up’ CRFs.

Date and cause of death will be provided in individual participant data listing together with selected dosing information (study intervention received, date of first/last administration, dose).

In addition, deaths due to COVID-19 may be presented in a separate listing if there is significant impact of COVID-19.

### **6.7.3. Laboratory Data**

Laboratory results will be converted to International System of Units (Système International d'unités, SI) units which will be used for applying toxicity grades and for all summaries.

As described in [Section 3.4](#), baseline will be defined as the last assessment performed on or prior to date of the first dose of study intervention. If there are multiple assessments that meet the baseline definition on the same day without the ability to determine which was truly last, then the worst grade will be assigned as the baseline grade.

Results collected as strict inequalities (eg,  $>10$ ,  $<10$ ) will be converted to numeric values adding or subtracting a factor of  $<0.001>$ . Expressions of the form “ $\geq$ ” or “ $\leq$ ” will be converted to the end point. These numeric values will be evaluated for clinically significant abnormalities, but will not be included in calculations of summary statistics.

Additionally, laboratory results will be programmatically classified according to NCI-CTCAE version 5.0 grade. Non-numerical qualifiers will not be taken into consideration in the derivation of grade (eg, hypokalemia Grade 1 and Grade 2 are only distinguished by a non-numerical qualifier and therefore Grade 2 will not be derived). In summary statistics the number and percentage of participants corresponding to grades that only include non-quantitative criteria will be displayed as a blank or NA (not assessed) rather than 0. If there is any overlap between grade criteria (eg, CTCAE grading criteria for Creatinine

Increased – a value can fall into one range based on comparison to Upper Limit of Normal (ULN) and another range based on comparison to baseline), the highest (worst) grade would be assigned to that record. Grade 5 is defined in the CTCAE criteria guidance as an event with an outcome of death. Since laboratory data does not collect an outcome, Grade 5 is not used when programmatically grading laboratory data.

For laboratory tests without CTCAE grade definitions, results will be categorized as normal, abnormal, or not done.

Grade 0 or Outside Toxicity Reference (OTR) is not defined specifically in the CTCAE guidance. However, programmatically this is used as a category to represent those participants who did not meet any of the Grades 1 to 4 criteria. If the laboratory value is evaluable for CTCAE criteria grading (numeric value is present, valid units and ranges are present as required to allow conversion to standard units and grading), and does not qualify for any of the Grade 1-4 criteria for a given lab test, then the value is assigned as Grade 0 or OTR.

Several of the CTCAE terms (including Hypo/Hypercalcemia, Chronic Kidney Disease, and Activated Partial Thromboplastin) can be derived using several laboratory tests (analytes).

For WBC differential counts (total neutrophil [including bands], lymphocyte, monocyte, eosinophil, and basophil counts), the absolute value will be used when reported by the lab and will be graded following the CTCAE guidance.

When only percentages are available (this is mainly applicable for neutrophils and lymphocytes, because the CTCAE grading is based on the absolute counts), the absolute value is derived as follows:

$$\text{Derived differential absolute count} = (\text{WBC count}) \times (\text{Differential \%value} / 100)$$

If the investigator reports both the absolute and % value for Neutrophils or Lymphocytes from the same laboratory sample date and participant, ONLY the absolute value will be graded. The % value will not be graded in this scenario.

If the % value is converted to the differential absolute count for grading and the Lower Limit of Normal (LLN) for the differential absolute count is not available (only LLN for % is available) then Grade 1 will be assigned if the following conditions are met:

- Lymphocyte count decreased:
  - derived absolute count does not meet Grade 2-4 criteria, and
  - % value < % LLN value, and
  - derived absolute count  $\geq 800/\text{mm}^3$ .

- Neutrophil count decreased:
  - derived absolute count does not meet Grade 2-4 criteria, and
  - % value < % LLN value, and
  - derived absolute count  $\geq 1500/\text{mm}^3$ .

For calcium, CTCAE grading is based on Corrected Calcium and Ionized Calcium. Corrected Calcium is calculated from Albumin and Calcium as follows:

$$\text{Corrected Calcium (mg/dL)} = \text{measured total calcium (mg/dL)} - 0.8 [\text{serum albumin (g/dL)} - 4]$$

Abnormalities will be described using the worst grade by scheduled timepoint and overall. Worst case overall will be determined using laboratory results from scheduled and unscheduled visits. Several laboratory tests have bi-directional grading criteria defined so that both low (hypo) and high (hyper) values can be graded separately. Each criterion will be summarized separately. In the cases where a value is graded as a Grade 1, 2, 3, or 4 for one of the directions, that value will also be assigned as a Grade 0 for the opposite direction for that test. For example, a value meeting the criteria for Grade 3 Hypercalcemia will be classified as a Grade 0 Hypocalcemia. For CTCAE terms that can be derived using one of several laboratory tests, the maximum postbaseline grade for a given participant and CTCAE term will be the maximum across all possible laboratory tests.

Additional laboratory results that are not part of NCI-CTCAE will be presented according to the following categories by scheduled timepoint as well as overall: below normal limit, within normal limits, and above normal limits. In the unlikely event that for a given participant, clinically significant abnormalities are noted in both directions (eg, > ULN and < LLN), then both abnormalities are counted.

The following summary tables will be created:

- Shift summary of laboratory parameters during the on-treatment period by maximum CTCAE grade;
- Shift summary of laboratory parameters from  $\leq$  Grade 2 at baseline to  $\geq$  Grade 3 post-baseline;
- Shift summary of laboratory test results with no CTCAE criteria by worst on-treatment assessment.

All laboratory test results will be presented in a data listing sorted by participant identifier, laboratory test, and date/time of collection. The CTCAE grades and the classifications relative to the laboratory reference ranges will be presented. Values outside laboratory normal ranges will be flagged where appropriate.

**Liver function tests:** Alanine aminotransferase (ALT), aspartate aminotransferase (AST), Alkaline Phosphatase (ALP), and total bilirubin (TBILI) are used to assess possible drug induced liver toxicity. The ratios of test result over the ULN will be calculated and classified for these 3 parameters during the on-treatment period.

Summary of liver function tests will include the following categories. The number and percentage of participants with each of the following during the on-treatment period will be summarized:

- $ALT \geq 3 \times ULN$ ,  $ALT \geq 5 \times ULN$ ,  $ALT \geq 10 \times ULN$ ,  $ALT \geq 20 \times ULN$
- $AST \geq 3 \times ULN$ ,  $AST \geq 5 \times ULN$ ,  $AST \geq 10 \times ULN$ ,  $AST \geq 20 \times ULN$
- $(ALT \text{ or } AST) \geq 3 \times ULN$ ,  $(ALT \text{ or } AST) \geq 5 \times ULN$ ,  $(ALT \text{ or } AST) \geq 10 \times ULN$ ,  $(ALT \text{ or } AST) \geq 20 \times ULN$
- $TBILI \geq 2 \times ULN$
- Concurrent  $ALT \geq 3 \times ULN$  and  $TBILI \geq 2 \times ULN$
- Concurrent  $AST \geq 3 \times ULN$  and  $TBILI \geq 2 \times ULN$
- Concurrent  $(ALT \text{ or } AST) \geq 3 \times ULN$  and  $TBILI \geq 2 \times ULN$
- Concurrent  $(ALT \text{ or } AST) \geq 3 \times ULN$  and  $TBILI \geq 2 \times ULN$  and  $ALP \geq 2 \times ULN$
- Concurrent  $(ALT \text{ or } AST) \geq 3 \times ULN$  and  $TBILI \geq 2 \times ULN$  and  $ALP \leq 2 \times ULN$  or missing

Concurrent measurements are those occurring on the same date.

Categories will be cumulative, ie, a participant with an elevation of  $AST \geq 10 \times ULN$  will also appear in the categories  $\geq 5 \times ULN$  and  $\geq 3 \times ULN$ . Liver function elevation and possible Hy's Law cases will be summarized using frequency counts and percentages.

An evaluation of Drug-Induced Serious Hepatotoxicity (eDISH) plot will also be created by graphically displaying:

- Peak serum ALT(/ULN) vs peak total bilirubin (/ULN) including reference lines at  $ALT = 3 \times ULN$  and total bilirubin =  $2 \times ULN$ .
- Peak serum AST(/ULN) vs peak total bilirubin (/ULN) including reference lines at  $AST = 3 \times ULN$  and total bilirubin =  $2 \times ULN$ .

In addition, the following listings of all TBILI, ALT, AST and ALP values will be provided:

- For participants with a postbaseline  $TBILI \geq 2 \times ULN$ ,  $ALT \geq 3 \times ULN$  or  $AST \geq 3 \times ULN$  and  $ALP \leq 2 \times ULN$  at any timepoint;

- For participants with a postbaseline  $TBILI \geq 2 \times ULN$ ,  $ALT \geq 3 \times ULN$  or  $AST \geq 3 \times ULN$  and  $ALP \leq 2 \times ULN$  at the same visit.

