10.6. Appendix 6: Liver Safety: Suggested Actions and Follow-Up Assessments

Potential Cases of Drug-Induced Liver Injury

Humans exposed to a drug who show no sign of liver injury (as determined by elevations in transaminases) are termed “tolerators,” while those who show transient liver injury but adapt are termed “adaptors.” In some participants, transaminase elevations are a harbinger of a more serious potential outcome. These participants fail to adapt and therefore are “susceptible” to progressive and serious liver injury, commonly referred to as DILI. Participants who experience a transaminase elevation above $3 \times \text{ULN}$ should be monitored more frequently to determine if they are “adaptors” or are “susceptible.”

In the majority of DILI cases, elevations in AST and/or ALT precede TBili elevations ($>2 \times \text{ULN}$) by several days or weeks. The increase in TBili typically occurs while AST/ALT is/are still elevated above $3 \times \text{ULN}$ (ie, AST/ALT and TBili values will be elevated within the same laboratory sample). In rare instances, by the time TBili elevations are detected, AST/ALT values might have decreased. This occurrence is still regarded as a potential DILI. Therefore, abnormal elevations in either AST OR ALT in addition to TBili that meet the criteria outlined below are considered potential DILI (assessed per Hy’s Law criteria) cases and should always be considered important medical events, even before all other possible causes of liver injury have been excluded.

The threshold of laboratory abnormalities for a potential DILI case depends on the participant’s individual baseline values and underlying conditions. Participants who present with the following laboratory abnormalities should be evaluated further as potential DILI (Hy’s law) cases to definitively determine the etiology of the abnormal laboratory values:

- Participants with AST/ALT and TBili baseline values within the normal range who subsequently present with AST OR ALT values $>3 \times \text{ULN}$ AND a TBili value $>2 \times \text{ULN}$ with no evidence of hemolysis and an alkaline phosphatase value $<2 \times \text{ULN}$ or not available.

For participants with baseline AST OR ALT OR TBili values above the ULN, the following threshold values are used in the definition mentioned above, as needed, depending on which values are above the ULN at baseline:

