- Preexisting AST or ALT baseline values above the normal range: AST or ALT values >2 times the baseline values AND $>3 \times \text{ULN}$; or $>8 \times \text{ULN}$ (whichever is smaller).
- Preexisting values of TBili above the normal range: TBili level increased from baseline value by an amount of at least $1 \times \text{ULN}$ or if the value reaches $>3 \times \text{ULN}$ (whichever is smaller).

Rises in AST/ALT and TBili separated by more than a few weeks should be assessed individually based on clinical judgment; any case where uncertainty remains as to whether it represents a potential Hy's Law case should be reviewed with the sponsor.

The participant should return to the investigator site and be evaluated as soon as possible, preferably within 48 hours from awareness of the abnormal results. This evaluation should include laboratory tests, detailed history, and physical assessment. The possibility of hepatic neoplasia (primary or secondary) should be considered.

In addition to repeating measurements of AST and ALT and TBili for suspected Hy's Law cases, additional laboratory tests should include albumin, CK, direct and indirect bilirubin, GGT, PT/INR, total bile acids, and alkaline phosphatase. Consideration should also be given to drawing a separate tube of clotted blood and an anticoagulated tube of blood for further testing, as needed, for further contemporaneous analyses at the time of the recognized initial abnormalities to determine etiology. A detailed history, including relevant information, such as review of ethanol, acetaminophen/paracetamol (either by itself or as a coformulated product in prescription or over-the-counter medications), recreational drug, or supplement (herbal) use and consumption, family history, sexual history, travel history, history of contact with a jaundiced person, surgery, blood transfusion, history of liver or allergic disease, and potential occupational exposure to chemicals, should be collected. Further testing for acute hepatitis A, B, C, D, and E infection, liver imaging (eg, biliary tract), and collection of serum samples for acetaminophen/paracetamol drug and/or protein adduct levels may be warranted.

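### The master SAP tabulates combined ALT/AST and bilirubin elevations only when they share a date, so its table can miss a sequential case that Protocol Appendix 6 still treats as potential DILI.

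*SAP*

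**What the plan says.** Master SAP 6.7.3 (Laboratory Data, liver function tests) has five rows that combine ALT or AST with total bilirubin. All five are labelled concurrent, and the section explains: "Concurrent measurements are those occurring on the same date". It then states: "Liver function elevation and possible Hy's Law cases will be summarized using frequency counts and percentages". It gives no separate definition of a possible Hy's Law case, so the concurrent rows are the only candidates for that count.

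The same section plans two displays without a same-date condition. The eDISH plots show "Peak serum ALT(/ULN) vs peak total bilirubin (/ULN) including reference lines at" 3×ULN for ALT and 2×ULN for bilirubin, with a matching AST plot. For listings it says: "In addition, the following listings of all TBILI, ALT, AST and ALP values will be provided", one selecting participants at any timepoint and one at the same visit.

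Protocol Appendix 6 (Section 10.6) describes the usual pattern as overlapping: "AST/ALT and TBili values will be elevated within the same laboratory sample". It then adds: "In rare instances, by the time TBili elevations are detected, AST/ALT values might have decreased". Its ruling on that pattern is "This occurrence is still regarded as a potential DILI". Only a wide separation leaves the automatic definition: "Rises in AST/ALT and TBili separated by more than a few weeks should be assessed individually based on clinical judgment".

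Both sub-study SAPs (Section 6.7 in each) refer to the master SAP for safety summaries.

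**The concern.** The protocol and the SAP use different timing rules for the same concept. A transaminase peak followed a week later by a bilirubin rise, with transaminases already below threshold, is potential DILI under Appendix 6 and absent from the SAP's combined rows. In a small early-phase combination study a single such participant matters. A table showing zero could be read as showing that no participant met the protocol's criteria, when it shows only that none met them on one date. In Sub-study B dose expansion, laboratory abnormalities, including their frequency and timing, are a primary endpoint.

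**Working it through.** The documents state no expected number of Hy's Law cases, so there is no figure to reproduce. The check compares the rules and applies them to assumed profiles.

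**Rules, in multiples of ULN**

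- SAP same-date row (6.7.3): on some one date, ALT or AST ≥3, TBILI ≥2, and ALP ≤2 or missing.
- SAP peak view (eDISH): maximum ALT (or AST) ≥3 and maximum TBILI ≥2, on any dates.
- Appendix 6, normal baseline: AST or ALT >3, TBILI >2, ALP <2 or not available, no hemolysis. The two rises need not coincide.
- Appendix 6, raised AST/ALT baseline b: more than 2b and more than 3, or more than 8, whichever is smaller.
- Appendix 6, raised TBILI baseline: a rise of at least 1, or a value above 3, whichever is smaller.

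**Assumed profiles** (ALP 1, no hemolysis, baselines normal unless stated)

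| Profile | SAP same-date row | SAP peak view | Appendix 6 |
|---|---|---|---|
| 1. Day 15: ALT 4, TBILI 1. Day 22: ALT 2, TBILI 2.5 | not counted | shown | potential DILI |
| 2. One date: ALT 4, TBILI 2.5 | counted | shown | potential DILI |
| 3. Baseline ALT 2; one date: ALT 3.5, TBILI 2.5 | counted | shown | not met (ALT must exceed 2 × 2 = 4) |
| 4. Baseline TBILI 1.4; one date: ALT 3.5, TBILI 2.2 | counted | shown | not met (TBILI must reach 1.4 + 1 = 2.4) |
| 5. One date: ALT 3.0, TBILI 2.0 | counted | shown | not met (both must be strictly above) |

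Profile 1 is the gap. The rises are 22 − 15 = 7 days apart, well inside a few weeks.

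**Direction.** At fixed thresholds, anyone meeting the same-date rule also meets a windowed rule, so the same-date rule can only lower the count. At fixed timing, anyone meeting Appendix 6 also meets the SAP thresholds. The SAP uses ≥ rather than >, allows ALP equal to 2×ULN, makes no baseline adjustment and has no hemolysis exclusion, so its thresholds can only raise the count. Profile 1 shows the first effect and profiles 3 to 5 the second. The documents do not say which would dominate.

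**Size of one case.** Sub-study A Phase 2, about 50 participants: 1/50 = 2 percentage points. Sub-study B expansion, up to 20 at the RP2D: 1/20 = 5 percentage points.

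**A related gap in the listings.** The table accepts ALP ≤2×ULN or missing, and Appendix 6 accepts ALP not available. The two listings require ALP ≤2×ULN with no provision for missing values. A sequential case with no ALP result would be absent from both table and listing, and would appear only as a point on the plot.

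**The case against.** The strongest reply is that little is lost. Appendix 6 calls the sequential pattern rare and expects both elevations in one sample as a rule. It asks for closer monitoring once transaminases pass 3×ULN and for evaluation preferably within 48 hours, and master SAP 5.2.11 uses unscheduled results for worst-case safety values. The eDISH plots and any-timepoint listing already show these participants, and with about 50 people the upper-right quadrant can be counted by eye. A case reported as an SAE would also enter the serious TEAE summaries if treatment-emergent. All of this stands, and it limits the point. It does not close the gap: none of these outputs counts possible Hy's Law cases, and none applies the protocol's distinction between nearby and widely separated rises.

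Three stronger readings are tempting, and the documents do not support them.

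- A reader might infer that the tabulated number will always be too low. The looser thresholds can push it the other way, and if no sequential case occurs the same-date rule loses nothing.
- A reader might expect the table to match the SAE reports. Appendix 6 makes a case reportable once repeat testing confirms it and no other reason has been found. The table is a laboratory screen without those conditions, so the two counts were not built to agree.
- A reader might try to put a capture rate on the same-date rule. That needs an overlap duration and a sampling schedule. The documents supplied give no overlap duration, and the sub-study schedules are not among them.

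The version caveat also stands. The supplied master SAP rests on protocol Amendment 1, while the protocol text is from October 2023. The sub-study SAPs cite master SAP Section 6.6 for safety, which is 6.7 in this copy. A later master SAP may exist and may treat this differently.

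**Conclusion.** The point holds as a mismatch in timing rules. As written, the master SAP's frequency table can miss a sequential case that Appendix 6 still regards as potential DILI, and no other planned output counts it. The pattern is described as rare, and the participant would usually still be visible in the plot or listing. Each missed case is worth 2 percentage points at n = 50 and 5 at n = 20. The net direction of error against Appendix 6 is not determined. The conclusion assumes that the concurrent rows are the intended count of possible Hy's Law cases, since none other is defined, and that the supplied master SAP is the one in force. It concerns reporting: evaluation and reporting of individual cases run through Appendix 6 and do not depend on this table.

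**What to change.** In master SAP 6.7.3:

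1. Define a possible Hy's Law case explicitly.
2. Beside the same-date rows, add a row counting participants with ALT or AST ≥3×ULN and TBILI ≥2×ULN on that date or within a set number of days after it, with ALP ≤2×ULN or missing. The sponsor should prespecify the window, consistent with the few weeks in Appendix 6, and say which ALP value is used.
3. Add missing ALP to both listings.
4. Reconcile the strict and non-strict inequalities, the ALP bound, the baseline-adjusted thresholds and the hemolysis condition with Appendix 6, or state that the table is a deliberately broader screen.
5. Check any later master SAP for the same rule.

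The new row uses data already collected and costs one more derivation. The downside is a few extra participants to review, some of whom will have another cause for the abnormal values.
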